15.1.3. PRIMARY ANALYSIS OF PRIMARY EFFICACY VARIABLE

The treatment effect on the primary efficacy endpoint will be estimated using an MMRM method. The model will include the change from baseline at each pre-specified time point as the response variable, study visit, Bipolar Disorder stratification variable at screening (Bipolar I

Document: ...\ITI\ITI-007\MYA11638\Biostatistics\Documentation\SAP\ITI-007-404 SAP Final V1.0 12JUN2019.docx
Author: Version Number:1.0

Version Number 1.0

Page 24 of 53

or Bipolar II), treatment (60 mg ITI-007 or placebo) and site (or pooled site) as factors, baseline MADRS total score as covariate and interaction terms for baseline MADRS total score-by-study visit and treatment-by-study visit. The subject term will be included in the model as a random effect while all other terms will be considered fixed effects. An unstructured covariance matrix will be used to model the correlation among repeated measurements within subject.

The Kenward-Rogers method will be used to estimate the denominator degrees of freedom. The treatment and treatment-by-study visit interaction terms allow for comparisons of the treatment groups at the time point of interest (Days 8, 15, 22, 29, 36 and 43). Treatment differences will be evaluated via contrasts for the study visit-by-treatment factor.

The change from baseline to Day 43 will be used for the primary efficacy analysis, and will be performed for the ITT Set

Summary statistics for change from baseline in MADRS total score will be presented by treatment group and study visit (Day), as well as least-squares mean (LSM) estimates. standard errorsand the corresponding 95% CI for LSMs.Contrast estimates (LSM differences) for between-group comparison, the corresponding standard errors, 95% CIs, effect sizes, and p-values will also be presented for each study visit (Day). Effect size will be calculated for the ITI-007 60 mg treatment group as:

LS Mean Difference

Pooled estimate of within subject error standard deviation

15.2. **KEY SECONDARY EFFICACY ENDPOINT**

The key secondary efficacy endpoint is the change from baseline to Day 43 in the Clinical Global Impression scale, Bipolar Version, for Severity (CGI-BP-S).

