The CGI-BP-S is a single value assessment of illness severity in mania, depression and overall bipolar illness and ranges from 1='Normal, not at all ill' to 7='Very severely ill' It is used in this study at screening (as a criterion for inclusion or exclusion), at baseline, and throughout the study, at Days 8, 15, 22, 29, 36, and 43. A higher score is associated with greater illness severity. The CGI-BP-S has 3 subscales, one each for mania, depression and overall bipolar illness. These 3 subscales are included in the calculation of the CGI-BP-S total score which will be recorded on the Clinical Global Impressions – Bipolar (CGI-S-BP) CRF page.

...\ITI\ITI-007\MYA11638\Biostatistics\Documentation\SAP\ITI-007-404 SAP Final V1.0 12JUN2019.docx Document: Author:

[figure not shown]
Version Number:1.0

Page 25 of 53

Change from baseline in the CGI-BP-S total score will be evaluated using an MMRM method similar to the one specified for the primary analysis of the primary efficacy endpoint, where the change from baseline to each pre-specified time point in CGI-BP-S total score is the response variable, study visit, Bipolar Disorder stratification variable at screening (Bipolar I or Bipolar II), treatment (60 mg ITI-007 or placebo) and site (or pooled site) as factors, baseline CGI-BP-S total score as covariate and interaction terms for baseline CGI-BP-S total score-by-study visit and treatment-by-study visit. The subject term will be included in the model as a random effect while all other terms will be considered as fixed effects. See Section 15.1.3, the primary analysis of primary efficacy endpoint, for more details.

Document:

...\ITI\ITI-007\MYA11638\Biostatistics\Documentation\SAP\ITI-007-404 SAP Final V1.0 12JUN2019.docx

Author:

Version Number: 1.0

Page 26 of 53

Document:

...\ITI\ITI-007\MYA11638\Biostatistics\Documentation\SAP\ITI-007-404 SAP Final V1.0 12JUN2019.docx

Author:

Version Number:1.0

Version Date: 12JUN2

STATISTICAL ANALYSIS PLAN: PROTOCOL ITI-007-404
Page 27 of 53

Document: Author: ...\ITI\ITI-007\MYA11638\Biostatistics\Documentation\SAP\ITI-007-404 SAP Final V1.0 12JUN2019.docx

or: Version Number:1.0

Version Date: 12JUN2019

Document:

...\ITI\ITI-007\MYA11638\Biostatistics\Documentation\SAP\ITI-007-404 SAP Final V1.0 12JUN2019.docx

Author:

Version Number:1.0

Version Date: 12JUN2019

[figure not shown]

Document: Author: ...\ITI\ITI-007\MYA11638\Biostatistics\Documentation\SAP\ITI-007-404 SAP Final V1.0 12JUN2019.docx

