The analysis of change from baseline in all vital sign measurements to Day 43 will be performed using an MMRM method. The model will include visit. Bipolar Disorder stratification variable at screening (Bipolar I or Bipolar II), site (or pooled site) and treatment as factors, baseline values as covariate and interaction terms for baseline baseline value-by-study visit. The subject term will be included in the model as a random effect while all other terms will be considered fixed effects. Summary statistics for change from baseline will be presented by treatment group and study visit (Day) as well as LSM estimates and the the associated standard error.LSM differences between 60mg ITI-007 and placebo, the associated standard errors, 95% CIs and p-values for between-treatment tests of differences will be presented for each study visit (Day).

As an exploratory analysis, change from baseline in these vital signs to each assessment time point will also be evaluated using an ANCOVA with LOCF model with effects for study visit. baseline value, Bipolar Disorder stratification variable at screening (Bipolar I or Bipolar II), site (or pooled site) and treatment. LSMs and the associated standard errors for each treatment group (ITI-007 60 mg or placebo), the LSM differences for between-treatment comparisons (ITI-007 60 mg vs. placebo), the corresponding standard errors, 95% CIs and p-values for the between-treatment differences will be presented for each assessment time point.

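### SAP 16.4 names no covariance structure and no treatment-by-visit term for the vital-signs MMRM, yet orders a treatment comparison at every visit; the two gaps need one joint edit

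*SAP*

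**What the plan says.** SAP 16.4 sets the lead analysis: "The analysis of change from baseline in all vital sign measurements to Day 43 will be performed using an MMRM method". The factors are visit, Bipolar I/II stratum, site and treatment. The baseline value is a covariate, and the text goes on with "interaction terms for baseline baseline value-by-study visit. The subject term will be included in the model as a random effect", all other terms being fixed. It says nothing more on dependence within a patient. It then orders LSMs with standard errors for each arm and visit, LSM differences with standard errors and 95% CIs, and "p-values for between-treatment tests of differences will be presented for each study visit (Day").

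The two efficacy MMRMs are fuller. SAP 15.1.3 has the same random-subject sentence but follows it with "An unstructured covariance matrix will be used to model the correlation among repeated measurements within subject", and it names Kenward-Roger degrees of freedom. Its fixed effects include "interaction terms for baseline MADRS total score-by-study visit and treatment-by-study visit", and it says that the treatment and treatment-by-visit terms are what allow comparison at each time point. SAP 15.2 (CGI-BP-S) repeats the random-subject sentence, lists both interactions, and adds "See Section 15.1.3, the primary analysis of primary efficacy endpoint, for more details". Section 16.4 has none of these: no matrix, no degrees-of-freedom method, no treatment-by-visit term and no cross-reference.

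**The concern.** A programmer who codes 16.4 as it stands fits a random intercept with independent residuals. That is compound symmetry: one variance for all six on-treatment visits and one correlation for every pair of visits. If the spread of change from baseline differs between visits, as is plausible for weight, a pooled variance cannot be right at each visit.

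The same sentence also leaves out the term that makes a treatment difference specific to a visit. The model cannot deliver what the paragraph orders, so someone will have to repair it. If the repair is only to add the interaction, the pooled variance feeds directly into the by-visit treatment comparisons.

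Change in vital signs is a named safety objective (Protocol 3.1.2.3, SAP 3.2.3). At stake are how the end-of-treatment weight comparison is read and whether an early change can be seen. A further risk is that the covariance gets chosen at programming, possibly after unblinding.

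**Working it through.** The plan gives no figure for this model, so there is none of its own to reproduce. The check compares a random-intercept fit with an assumed true covariance.

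**Inputs from the documents.** Six on-treatment visits, Days 8, 15, 22, 29, 36 and 43 (SAP 16.4); two-sided 5% tests (SAP 7); 163 evaluable patients per arm (Protocol 12.1). The ratios below do not depend on n.

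**Assumed.** Complete data. SD of change rising linearly from 1 at Day 8 to r at Day 43, with r from 1 to 3. AR(1) correlation of 0.7 between adjacent visits, needed only for steps 1 and 3.

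**Notation.** v_t is the variance at visit t, v̄ the mean of the six variances, S the true covariance matrix, and q = w'Sw with every weight 1/6. With balanced data the random-intercept fit estimates the total variance at every visit as v̄.

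**Step 1. Model as written (no treatment-by-visit).** There is one treatment difference, the average over visits. Its true variance is (2/n)q. The model's variance is (2/n)(s_b² + s_e²/6), with s_b² the mean covariance and s_e² = v̄ − s_b², which equals (2/n)q. The ratio of model to true SE is 1.000 for every r tried. The estimate, SE, CI and p-value are the same at all six visits.

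A per-arm LSM at visit t is the visit mean over both arms plus or minus half that difference. Its true variance is (v_t + q)/(2n), against (v̄ + q)/(2n) in the model. At r = 2, v̄ = 2.367 and q = 1.291:
- Day 8: √[(2.367 + 1.291)/(1 + 1.291)] = 1.26
- Day 43: √[(2.367 + 1.291)/(4 + 1.291)] = 0.83

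At r = 1.5 the ratios are 1.15 and 0.89. At r = 1 both are 1.00.

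**Step 2. Interaction added, random intercept kept.** The between-group SE ratio at visit t is √(v̄/v_t). True alpha at Day 43 is 2[1 − Φ(1.96 × ratio)]. Example, r = 2: the variances 1, 1.44, 1.96, 2.56, 3.24 and 4 sum to 14.2, so v̄ = 2.367. The Day 43 ratio is √(2.367/4) = 0.77, and the Day 8 ratio is √2.367 = 1.54.

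| r (assumed) | v̄ | Day 8 ratio | Day 43 ratio | True alpha, Day 43 |
|---|---|---|---|---|
| 1.00 | 1.000 | 1.00 | 1.00 | 5.0% |
| 1.25 | 1.273 | 1.13 | 0.90 | 7.7% |
| 1.50 | 1.592 | 1.26 | 0.84 | 9.9% |
| 2.00 | 2.367 | 1.54 | 0.77 | 13.2% |
| 3.00 | 4.467 | 2.11 | 0.70 | 16.7% |

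**Step 3. Covariance changed, interaction still missing.** The single treatment effect becomes a generalised least-squares average with visit weights proportional to S⁻¹1. At r = 2, Day 8 gets 71% of the weight and Day 43 about 9%. Under a random walk (variance proportional to time), Day 8 gets 100%. A late weight change would almost vanish from the estimate.

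**Simulation.** 60 trials, 163 per arm, r = 2, assumed 15% dropout, true differences 0.10 at Day 8 and 0.60 at Day 43. As written, the one estimate averaged 0.36 (mean SE 0.126, empirical SD 0.136). With the interaction and a random intercept, the estimates averaged 0.113 at Day 8 and 0.610 at Day 43, near the truth. The SEs were not: 0.168 against an empirical 0.113 at Day 8, and 0.178 against 0.257 at Day 43.

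**The case against.** The strongest reply is that 16.4 is silent on covariance and does not choose compound symmetry. It calls the analysis an MMRM, and in 15.1.3 the same random-subject sentence stands next to an unstructured matrix, so in this SAP the sentence does not exclude one. SAP 7 also points to a sequence of correlation structures in 15.1.3, and nothing shows that the simplest was meant for vital signs. This stands: the fault is under-specification, and compound symmetry is what follows from a literal coding.

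A reader might go further and infer that, as planned, the weight comparison at Day 43 has too small a standard error and an inflated alpha. The documents do not support that. Without treatment-by-visit there is no separate Day 43 difference, and with complete data the SE of the common difference is correct (ratio 1.000). The figures in step 2 belong to a partly repaired model and also need an SD of weight change that grows over visits, for which the documents give no value.

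A similar inference for blood pressure is that Day 43 is an average over positions while Days 8 to 36 are single readings. SAP 16.4 and Protocol 8.1.5 say which visits have 3-positional readings, but not how many readings are taken at the others.

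On consequence, the protocol's safety analysis text (under 12.4.4) calls any treatment-group comparison in its laboratory, vital-sign and ECG paragraph exploratory. The by-visit descriptive summaries and the incidence of weight change of 7% or more do not use this model. That stands too and limits the weight of the point. Against it, SAP 16.4 labels only the ANCOVA with LOCF as exploratory, so the MMRM is in practice the lead analysis of a stated safety objective.

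**Conclusion.** The concern holds as a joint specification gap in 16.4. As written, the model returns one treatment difference for all visits although a difference at each visit is promised. In the 2-fold simulation that one figure was 0.36, where the truth ran from 0.10 to 0.60. Its per-arm standard errors are wrong if variance changes over visits: 1.26 times the true value at Day 8 and 0.83 times at Day 43 for an assumed 2-fold SD growth.

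The between-group standard errors become wrong only when the interaction is added and the random intercept is kept. The size then depends wholly on the assumed SD growth and is nil if variance is constant. No confirmatory conclusion of the trial depends on it. It is still worth correcting, because the paragraph cannot be run as intended without a choice that the SAP should make before unblinding.

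**What to change.** Make one edit to SAP 16.4 with two parts:

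1. Add treatment-by-study visit to the interaction terms, next to baseline value-by-study visit.
2. Replace the random-subject sentence with: *Within-subject correlation will be modelled with an unstructured covariance matrix over the visits, with Kenward-Roger degrees of freedom, as in Section 15.1.3.* All listed terms stay fixed effects.

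The second part must not be made without the first: step 3 shows that it would put 71% to 100% of the weight for the single treatment effect on Day 8. The first without the second leaves the standard-error problem of step 2.

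The cost is one or two SAP sentences. Over six visits an unstructured matrix has 6 × 7/2 = 21 parameters against 2 for compound symmetry, so 19 more, which is small with about 350 patients. No data collection changes.

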16.4.1. VITAL SIGNS MARKEDLY ABNORMAL CRITERIA

Markedly abnormal quantitative vital signs measurements will be identified in accordance with the following predefined markedly abnormal criteria in the table below.

...\ITI\ITI-007\MYA11638\Biostatistics\Documentation\SAP\ITI-007-404 SAP Final V1.0 12JUN2019.docx Document: Author:

Page 39 of 53

Table H: Markedly Abnormal Criteria for Vital Signs

| Variable | Unit | Low | High |
|------------|------|--|---|
| SBP | mmHg | < 90 mmHg AND | > 180 mmHg AND |
| | | decrease from baseline ≥ 20 mmHg | increase from baseline ≥ 20 mmHg |
| DBP | mmHg | < 50 mmHg AND | > 105 mmHg AND |
| | | decrease from baseline | increase from baseline ≥ 15 |
| | | ≥ 15 mmHg | mmHg |
| Pulse rate | bpm | < 50 bpm AND | > 120 bpm AND |
| | | decrease from baseline ≥ 15 bpm | increase from baseline ≥ 15 bpm |
| Weight | Kg | percentage change from baseline ≤ -7.0 % | percentage change from baseline ≥ 7.0 % |

16.5. Modified Physical and Neurological Examination

The following summaries will be provided for physical examination data:

- Incidence of abnormalities at screening (baseline)
- Incidence of abnormalities post baseline

A modified physical examination, including neurological and excluding genital/rectal examinations, will be performed during screening, on Day 43 or Early Termination Visit and on Day 57 for all subjects. The examination should include evaluation of general appearance; eyes, ears, nose, and throat; skin; head and neck; lungs and chest; heart; abdomen; and extremities. Neurological examinations include an assessment of motor function, sensory function, reflexes, and gait. All physical and neurological examination findings are recorded in the eCRF.

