3.2.3. SAFETY SECONDARY OBJECTIVES

The safety secondary objectives of this study are to determine the safety and tolerability of lumateperone, administered orally once daily for 6 weeks in subjects with Bipolar Depression, compared to placebo. Safety and tolerability will be assessed in relation to:

- Incidence of adverse events (AEs);
- Mean change from baseline in the Young Mania Rating Scale (YMRS);
- Mean change from baseline in the Columbia Suicide Severity Rating Scale (C-SSRS);
- Mean change from baseline in the Abnormal Involuntary Movement Scale (AIMS);
- Mean change from baseline in the Barnes Akathisia Rating Scale (BARS);
- Mean change from baseline in the Simpson Angus Scale (SAS);
- Changes from baseline in clinical laboratory evaluations;
- Changes from baseline in electrocardiograms (ECGs);
- Changes from baseline in vital sign measurements;
- Physical and neurological examination findings.

Document: Author:

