16.1.4. ABUSE-RELATED TEAES

TEAEs will be categorized as defined in the table below to monitor signals of potential abuse of ITI-007. The number and percentage of subjects with at least one abuse-related TEAE will be summarized by category and the applicable PTs below.

Table D: Abuse-Related PTs

| Category | Applicable Preferred Terms |
|---|---|
| Euphoria | Euphoric mood; Elevated mood; Feeling abnormal; Feeling drunk; Feeling of relaxation; Dizziness; Thinking abnormal; Hallucination; Inappropriate affect |
| Impaired attention, cognition, and mood | Somnolence; Sedation; Mood disorders and disturbances |
| Dissociative/psychotic | Psychosis; Aggression; Confusion and disorientation |
| Other related terms | Drug tolerance; Habituation; Drug withdrawal syndrome; |

Document: Author: ...\ITI\ITI-007\MYA11638\Biostatistics\Documentation\SAP\ITI-007-404 SAP Final V1.0 12JUN2019.docx

Version Number:1.0

Version Date: 12JUN2019

Page 33 of 53

| Substance-related disorders |
|-----------------------------|
| |

16.2. **LABORATORY EVALUATIONS**

Results from the central laboratory will be included in the reporting of this study for hematology, clinical chemistry, urinalysis and screening serology. A list of laboratory assessments to be included in the outputs is included in the protocol, Section 8.5. Summary statistics will be presented in standard international (SI) and US conventional units.

Quantitative laboratory measurements reported as "< X", i.e. below the lower limit of quantitation (BLQ), or "> X", i.e. above the upper limit of quantitation (ULQ), will be converted to X for the purpose of quantitative summaries, but will be presented as recorded, i.e. as "< X" or "> X" in the listings.

Blood samples for laboratory evaluations will be collected after an overnight fast (≥10 hours) during screening and on Days 8, 22, 43 and Day 57 safety follow-up or during the discontinuation visit. All non fasting results for glucose, insulin and triglycerides will be excluded from descriptive statistics but will appear in the data listings.

The following summaries will be provided for laboratory data:

- Actual and change from baseline by visit, and for last on-treatment assessment where applicable (for quantitative measurements)
- Incidence of abnormal values according to normal range criteria
- Shift from baseline according to normal range criteria (for quantitative measurements and categorical measurements)

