- Shift from baseline to each visit according to markedly abnormal criteria (for quantitative measurements and categorical measurements)
- Incidence of markedly abnormal results defined in Section 16.3.1
- Listing of subjects meeting markedly abnormal criteria

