16.4. VITAL SIGNS

The following vital signs measurements will be reported for this study:

- Systolic blood pressure (mmHg)
- Diastolic blood pressure (mmHg)
- Pulse rate (bpm)
- Respiratory rate (breaths/min)
- Oral temperature (⁰C)
- Height (cm) at screening
- Weight (kg)
- BMI (kg/m²) [calculated as weight (kg) / height (m)²]

Vital signs, including systolic blood pressure, diastolic blood pressure, pulse rate, respiratory rate, oral temperature and body weight, are recorded at screening, baseline and Days 8, 15, 22, 29, 36, 43 and 57At screening, baseline and days 43 and 57 vital signs include the 3-positional blood pressure and pulse rate will be measured after 10 minutes in the supine position, 1-minute sitting, immediately after standing, and 3 minutes after standing at screening, baseline, day 43 and day 57. These 3-positional results will be averaged at each visit and used for the summary and analyses. Pulse will be measured by counting pulse over 60 seconds. Height will be measured only at screening.

BMI measurements classify a subject's weight status as underweight, normal, overweight, or obese using Table G:. Shifts from Baseline to Day 43 will be produced by treatment group for the SAF Set to show the percentage of subjects who fall into each BMI category combination.

Document: ...\ITI\ITI-007\MYA11638\Biostatistics\Documentation\SAP\ITI-007-404 SAP Final V1.0 12JUN2019.docx Author: Version Number:1.0

Page 38 of 53

Table G: **BMI Weight Status Categories**

| BMI (kg/m²) | Weight Status |
|-------------------|---------------|
| < 18.5 | Underweight |
| 18.5 ≤ BMI < 25.0 | Normal |
| 25.0 ≤ BMI < 30 | Overweight |
| 30.0 ≤ BMI | Obese |

The following summaries will be provided for vital sign data:

- Actual and change from baseline by visit
- Incidence of markedly abnormal values
- Listing of subjects meeting markedly abnormal criteria
- Shifts from baseline by visit and time point according to markedly abnormal criteria.
- BMI shift summaries

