The number and percentage of subjects with suicidality as measured by the C-SSRS will be summarized, where suicidality is defined as having at least one occurrence of suicidal ideation or at least one occurrence of suicidal behavior. The suicidality indicator will be set to 1 if the subject exhibits suicidality for each visit, 0 if the subject does not exhibit suicidality, and missing otherwise. This data will be summarized at each scheduled visit and overall by study period (treatment and post-treatment).

Data collected on actual suicide attempts (lethality of actual attempts and potential lethality of attempts) will be presented in a data listing.

An overall summary of C-SSRS data (post-baseline data across all scheduled visits) will include the frequency and percentage of the following:

- At least one suicidal ideation post-baseline
- Emergence of suicidal ideation (no suicidal ideation at baseline, and any type of suicidal ideation post-baseline)
- Emergence of serious suicidal ideation (no suicidal ideation at baseline, and any serious suicidal ideation [ideation score of 4 or 5] post-baseline)
- Most severe type of ideation post-baseline

Author:

Document: ...\ITI\ITI-007\MYA11638\Biostatistics\Documentation\SAP\ITI-007-404 SAP Final V1.0 12JUN2019.docx

[figure not shown]
Version Number:1.0
Version Date: 12JUN2019

Page 42 of 53

- Worsening of suicidal ideation (most severe suicidal ideation post-Baseline was more severe than it was at baseline)
- o At least one suicidal behavior post-baseline
- Emergence of suicidal behavior (no suicidal behavior at baseline, and any type of suicidal behavior post-baseline)
- o At least one actual attempt post-baseline
- At least one interrupted attempt post-baseline
- At least one aborted attempt post-baseline
- o At least one preparatory acts or behaviors post-baseline
- o At least one instance of suicidality [any ideation or behavior] post-baseline
- Emergence of suicidality (no suicidality at baseline, and any suicidality postbaseline)
- Any completed suicides post-baseline

Document: Author: ...\ITI\ITI-007\MYA11638\Biostatistics\Documentation\SAP\ITI-007-404 SAP Final V1.0 12JUN2019.docx

Version Number:1.0

Page 43 of 53

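### SAP 16.5 plans only marginal counts of examination abnormalities, so it gives no aggregated view of physical and neurological findings that are new since screening

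*SAP*

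**What the plan says.** SAP 3.2.3 lists "Physical and neurological examination findings" among the safety secondary objectives.

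SAP 16.5 states that the examination "will be performed during screening, on Day 43 or Early Termination Visit and on Day 57 for all subjects". It names two outputs: the incidence of abnormalities at screening, which serves as baseline, and "Incidence of abnormalities post baseline". It gives no condition that a finding be absent at screening, no definition of a new or worsened finding, and no shift table.

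Other safety sections of the SAP do compare each patient with his or her own baseline:

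- Laboratory (16.2): "Shift from baseline according to normal range criteria".
- ECG (16.3): "Shift from baseline to each visit according to markedly abnormal criteria".
- Vital signs (16.4): "Shifts from baseline by visit and time point according to markedly abnormal criteria".
- C-SSRS (16.6.5): emergence categories that require no ideation, behaviour or suicidality at baseline.

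The protocol (Protocol Summary, and the Safety Analyses text within 12.4.4) says that safety data, examination findings included, are summarised by treatment arm and by visit. It has no emergence rule for examinations.

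**The concern.** In the first output the word incidence can only mean that an abnormality is present, because a finding at screening cannot be new on study drug. Carried to the second output, the same meaning counts a long-standing finding recorded at screening and again at Day 43 as a post-baseline abnormality.

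Two marginal counts do not show how many patients changed. Equal totals before and after could mean that nothing happened, or that some findings resolved while others appeared. Persisting findings also add the same background to both arms, which pulls the ratio between arms towards 1. What is at stake is whether the table written for this objective can show an increase in new signs.

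**Working it through.** The documents give no rate, sample size or power for examination findings, so there is no stated figure to reproduce. The check is a reading of the text plus an illustration.

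**Text.** Of the five domains compared here (laboratory, ECG, vital signs, C-SSRS, examinations), only examinations have neither a shift summary nor an emergence summary.

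**Inputs.** About 175 per arm: 350 randomised 1:1 (Protocol 12.1). The remaining inputs are assumptions:

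- q = share of patients whose screening abnormality is still recorded after baseline: 10%, 20% or 30%.
- New findings among the other patients: 2% on placebo, 6% on drug.

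**Formula.** In each arm, P(any abnormality post baseline) = q + (1 − q) × P(new).

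At q = 20%:

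- Placebo: 0.20 + 0.80 × 0.02 = 0.216.
- Drug: 0.20 + 0.80 × 0.06 = 0.248.
- Difference: 3.2 points, which is (1 − q) × 4.0 points. Ratio: 0.248 / 0.216 = 1.15.
- New findings only, among about 175 × 0.80 = 140 per arm: difference 4.0 points, ratio 3.0.

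As a yardstick for lost contrast, the table gives the power of a two-sided 0.05 Fisher exact test by exact enumeration. The new-only column uses the reduced denominator.

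| q | Any abnormality, drug vs placebo | Ratio | Power, any (175 per arm) | Power, new only (n per arm) |
|---|---|---|---|---|
| 10% | 15.4% vs 11.8% | 1.31 | 13% | 33% (158) |
| 20% | 24.8% vs 21.6% | 1.15 | 9% | 28% (140) |
| 30% | 34.2% vs 31.4% | 1.09 | 7% | 23% (122) |

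With a larger assumed effect, 8% versus 2%, and q = 20%, the planned count gives 26.4% versus 21.6%, a ratio of 1.22 against 4.0 for new findings.

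The direction holds for any q above zero. The size depends on assumed rates. If counts are made within body systems, q is the share in that system, which cannot exceed the overall share, and the dilution is correspondingly no larger.

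**The case against.** The other side has several good points, and they limit the concern.

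- **Adverse events.** A reader might infer that a new sign reaches the adverse event tables only if the investigator judges it clinically significant. The documents do not support that. Protocol 9.1.10 requires all adverse events to be reported whatever their clinical significance, and 9.4 expects some to be discovered at physical examination. The significance filter in 8.5.1 concerns laboratory results and other safety assessments; its examples are ECGs and vital signs, not physical examinations. Under SAP 16.1 and 16.1.1, events that start or worsen after first dose are tabulated with relative risks. This backstop is real but partial. It depends on someone recording the sign as an event, and it closes one day after the last dose.
- **Visits.** A reader might infer that Day 43/early termination and Day 57 are pooled. SAP 16.5 does not say so, and the protocol calls for summaries by visit. The SAP simply does not repeat that here.
- **Tracing patients.** A reader might infer that patients with a new sign cannot be identified. SAP 8 provides subject listings of source data, so they can. Only the aggregated table is missing.
- **Other neurological data.** AIMS, BARS, SAS and the extrapyramidal query tables cover movement effects. Sensory function and reflexes, which SAP 16.5 includes in the examination, have no rating scale in the SAP.
- **Unstated rule.** The SAP does not say in words that pre-existing findings are counted. The table shells referred to in SAP 8 are not among the documents and could contain a rule. If they do, the SAP text should state it.

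**Conclusion.** The point holds as a minor improvement. On a plain reading, SAP 16.5 provides no aggregated summary of new examination findings, although the SAP provides the equivalent for laboratory, ECG, vital-sign and C-SSRS data.

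A reader might go further and infer a biased comparison. The documents do not support that. Randomisation balances pre-existing findings in expectation, the screening counts are tabulated so a chance imbalance would be visible, and no test of examination findings is planned. The consequence is reduced sensitivity of a descriptive display.

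On the assumed rates, the ratio between arms falls from 3.0 to between 1.09 and 1.31, while the absolute difference falls only from 4.0 points to between 2.8 and 3.6. The power figures illustrate lost contrast and do not describe a planned analysis. Even the count of new findings reaches only 23% to 33%. All of this assumes the stated rates, persistence of the screening abnormality in the share q, and examination of all 175 patients per arm.

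**What to change.** Keep both planned counts in SAP 16.5. Add a shift table by treatment group, for each body system and each neurological domain (motor function, sensory function, reflexes, gait): normal or abnormal at screening against Day 43/early termination, and separately against Day 57. This also carries the protocol's summary by visit into the SAP. Beside it, report the incidence of new abnormalities, with patients normal at screening in that system or domain as the denominator.

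The new summary should be added, not substituted. A rule of normal at screening and abnormal afterwards, used alone, would lose the overall post-baseline counts and any new sign in a system already abnormal at screening.

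The cost is a few lines of SAP text and one table shell. The findings are already recorded in the eCRF, so no new data collection is needed.
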